A reverse-mirror Grisotti flap, also known as a Reverse-Bay of Bengal modification, is a variation of the Grisotti flap technique used in breast cancer surgery. It is designed to reconstruct defects in the central breast quadrant after a breast conservation surgery. This modification involves re-orienting the flap medially where it is dependent mainly on the perforators of internal mammary artery for blood supply, potentially offering better aesthetic results and more versatile and robust blood supply. The Grisotti flap, despite its well known utility, has limitations, particularly in patients with non-ptotic breasts, where it may lead to fullness laterally and suboptimal cosmesis, the Reverse Bay of Bengal modification of the Grisotti flap is designed to address these limitations by preserving chest wall perforators and avoiding excessive lateral bulging.¹¹ This technique hence offers a more cosmetic alternative for patients with central quadrant tumors requiring nipple-areola complex (NAC) excision.¹¹

OBJECTIVES:

To compare the outcome between grisotti flap versus reverse mirror grisotti flap in terms of flap viability, cosmetic outcome (visual analogue scale) and seroma formation.

OPERATIONAL DEFINITIONS:

1. Centrally located breast tumors (CLBT):

Tumors that are completely or partially located in the projection of the areola up to the chest wall and/or within 2 cm around the areola

2. Grisotti Flap:

The Grisotti flap is a local rotational flap used to reconstruct defects after removing a central breast cancer, often involving the nipple-areola complex (NAC). It uses tissue from the inferior pole of the breast to fill the central defect.

3. Reverse-Mirror Flap:

The reverse-mirror version is a modification where the flap is flipped and reoriented, using the internal mammary vessels as the primary blood supply.

4. Flap viability:

Absence of necrosis of new areola formed as seen clinically at 48 hours and 7th day postoperatively.

Flap viability categories:

A (None): No necrosis.

B (Color Change): Color change suggesting impaired perfusion or ischemic injury.

C (Partial Thickness): Partial thickness skin flap necrosis resulting in wound breakdown.

D (Full Thickness): Full thickness skin flap necrosis.

5. Cosmetic outcome:

Cosmetic outcome will be explained with VAS (visual analogue scale) by the patient. The scale will range from 0-10 with 0 being categorized as worst cosmetic outcome and 10 being categorized as best cosmetic outcome.

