6. Seroma formation:

Seroma formation is the visible swelling at the operative site which will be confirmed and quantified by ultrasound on 7th post operative day with volume more than 20ml.

HYPOTHESIS:

There is a difference in the outcome between Grisotti versus Reverse Mirror Grisotti flap in centrally located breast cancers.

MATERIAL AND METHODS:

STUDY DESIGN: Randomised Control Trial

SETTING: SURGICAL FLOOR, MAYO HOSPITAL LAHORE.

DURATION OF STUDY: 06 months after approval of synopsis.

SAMPLE SIZE: Sample size of 106 patients (53 patients in each group) is estimated by using 95% confidence level, 10% absolute precision with expected percentage satisfaction rate in group A as 90% and in group B as 95%.

$$n = \frac{Z_{1-\alpha/2}^2 (P_1(1-P_1) + P_2(1-P_2))}{d^2}$$

$$d^2$$

$$Z_{1-\alpha/2} = \text{confidence level } 95\% = 1.96$$

$$P_1 = \text{population proportion A} = 90\%^{14}$$

$$P_2 = \text{Population proportion B} = 95\%^8$$

$$d = \text{absolute precision } 10\%$$

SAMPLING TECHNIQUE: computer generated random table.

SAMPLE SELECTION:

Inclusion Criteria:

1. Diagnosed cases of breast cancer patients
2. Gender: Females
3. Age: 25-70 years
4. T1 (<2cm) and T2 (2-5cm) tumors with or without prior systemic therapy
5. Tumor located in the NAC or located within 2 cm of the edge of the areola

Exclusion Criteria:

1. Metastatic breast cancer
2. Inflammatory breast cancer
3. Patients not willing for post-operative radiotherapy
4. High tumour-breast ratio

DATA COLLECTION PROCEDURE:

The study approval will be taken from the Ethical Committee of the King Edward Medical University, Lahore and will be performed in accordance with the current revision of the Helsinki Declaration. Informed consent will be obtained from all individual participants with diagnosis of central quadrant breast tumors as per operational definition, and data will be collected on predesigned proforma. Patients will be divided into two groups, Grisotti flap (group A) and Reverse Mirror Grisotti Flap (group B). Patients will be recruited from OPD of Mayo hospital during the same study period.

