Patients fulfilling the inclusion criteria will be randomly divided into either group. Pre-operative marking will be done in standing position. All procedures will be done under general anesthesia. Circumareolar incision will be given for excision of tumor alongwith nipple areolar complex. New areola will be marked beneath the previous nipple areolar complex and de-epithelialisation of infra-neo-areolar skin will be done . In group A, the dermoglandular flap will be raised on infero-lateral perforators of intercostal arteries and will be rotated and advanced to fill the gap . In group B, the dermoglandular flap will be raised on the medial perforators of internal mammary artery and will be rotated and advanced to fill the defect. In both groups, glandular approximation will be done with vicryl 3-0 interrupted sutures and skin will be closed with prolene 4-0 subcuticular sutures. Axillary lymph node dissection or sentinel lymph node biopsy will be done as indicated in each patient.

Post operatively flap viability will be assessed at 48 hours and on 7th day. Cosmetic outcome will be assessed using visual analogue scale on 7th postoperative day. Seroma formation will be assessed on 7th day post-operatively.

DATA ANALYSIS PRODECURE:

All the collected data will be entered and analyzed by using Statistical Package for the Social Sciences (SPSS,25). Quantitative data (cosmetic outcome with VAS) will be expressed as mean (M) \pm S.D. Independent T test will be used for comparing means for cosmetic outcome. Qualitative data (tumor size, flap viability and seroma formation) will be expressed as frequencies and percentages. Chi square (χ^2) test will be used to compare between groups for qualitative data. The association between type of procedure used and clinical outcome variable will be assessed by using Odds Ratio (OR) with 95% confidence interval (CI). The P value will be considered significant if it is less than 0.05.

OUTCOME & UTILIZATION:

Breast conservation surgery is equivalent to mastectomy for early stage breast cancer patients. Central quadrant tumours can be treated with various oncoplastic techniques with a satisfactory aesthetic outcome and low morbidity. Grisotti flap and reverse mirror grisotti flap are the favourable viable surgical options for central quadrant breast tumours.

REFERENCES:

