15. Emiroğlu M, Sert İ, İnal A. The role of oncoplastic breast surgery in breast cancer treatment. *The journal of breast health*. 2015 ;11(1):1.

Data Collection Proforma

Sr. #: _____ Name: _____ Age: _____ Gender: _____

Marital status: _____ Education status: _____

Residence: _____ Contact #: _____ ,

History of smoking: yes/no, family history of any cancer:
 yes/no _____ 1st degree: _____ 2nd degree: _____ 3rd
 degree: _____, Caste: _____, children: _____ Breast fed: yes/no,

Age of menarche: _____, H/O contraceptive use: _____

Consanguineous marriage: yes/no _____

Menopause: yes/no H/O alcohol use: yes/no, H/O smoking:

Chronic liver disease: yes/no

Chronic renal failure: yes/no

Tuberculosis: yes/no

Inflammatory bowel disease: yes/no

Autoimmune disease: yes/no

Previously treated any cancer disease: yes/no

Breast cancer with pregnancy: yes/no

Diagnosis (histopathology) _____,

Histological grade: I _____, II _____, III _____

Receptors: ER _____ PR _____ Her 2 neu _____ others _____

Stage _____ Chemo status _____

Surgery type _____ Radiotherapy _____

Variable	Group A (grisotti flap)		Group B (reverse mirror grisotti flap)	
Flap viability (A-D)	At 48 hours	On 7 th post-op day	At 48 hours	On 7 th post-op day
Cosmetic outcome (visual analogue scale)				
Seroma formation On 7 th post-op day	Yes / No		Yes / No	

Informed Consent Form

COMPARISON OF OUTCOME BETWEEN GRISOTTI FLAP VERSUS REVERSE MIRROR GRISOTTI FLAP FOR CENTRAL QUADRANT BREAST TUMORS.

The doctor has explained me about my disease. The research modalities required for treating my tumour have been thoroughly explained to me. As this research work requires the utilization of either grisotti or reverse mirror grisotti flap technique, therefore I allow the doctor to utilize any of these procedures on me.

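### One hypothesis, three unranked outcomes each tested at 0.05, and no primary outcome to decide it

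*Protocol*

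**What the plan says.** The Objectives section sets out the comparison "in terms of flap viability, cosmetic outcome (visual analogue scale) and seroma formation", giving the three no order of importance. The Hypothesis section is one sentence: "There is a difference in the outcome between Grisotti versus Reverse Mirror Grisotti flap in centrally located breast cancers". It does not say which outcome is meant.

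The Data Analysis section assigns the tests. For cosmesis, "Independent T test will be used for comparing means for cosmetic outcome". Flap viability and seroma are treated as categorical: "Qualitative data (tumor size, flap viability and seroma formation) will be expressed as frequencies and percentages", and the chi-square "test will be used to compare between groups for qualitative data". One threshold covers everything: "The P value will be considered significant if it is less than 0.05". An odds ratio is also planned, for a clinical outcome variable that is not identified.

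The Sample Size section uses a different quantity, the "expected percentage satisfaction rate in group A as 90% and in group B as 95" per cent. Satisfaction does not appear in the objectives, the operational definitions, the analysis section or the data collection proforma.

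Flap viability is assessed at 48 hours and on day 7, and the proforma records it in four grades (A to D) at each time. The analysis section does not say which time point is compared.

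**The concern.** A confirmatory trial with one hypothesis needs one result, or one stated rule, that decides it. Here there are at least three tests at 0.05 and nothing that ranks them. If the procedures differ on seroma but not on VAS or viability, the protocol does not say whether the hypothesis is supported. The investigators would have to decide with the results in front of them.

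The sample-size paragraph is the usual place to find an implied primary outcome. Here it points to a fourth quantity. The nearest defined outcome is the 0–10 patient-rated VAS, but that is compared as a mean, and no cut-off turns it into a proportion satisfied.

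At stake are the freedom to pick the deciding outcome after the fact and, if that freedom is used to promote whichever result is significant, a false-positive rate for the hypothesis above the nominal 5%.

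**Working it through.** **Step 1. The protocol's own figure.** The inputs are Z = 1.96, P1 = 0.90, P2 = 0.95 and d = 0.10, all from the Sample Size section.

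n = 1.96² × (0.90×0.10 + 0.95×0.05) / 0.10² = 3.8416 × 0.1375 / 0.01 = 52.8, rounded up to 53 per group, 106 in total.

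The figure reproduces. It comes from the satisfaction proportions alone and has no power term, so it is not tied to any of the three analysed outcomes.

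**Step 2. Search for a ranking.** The objectives, hypothesis, operational definitions, sample size, analysis section and proforma name no primary outcome, testing order or decision rule.

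**Step 3. Illustration: the false-positive rate if any one significant result counts.** The protocol does not state this rule, but it does not exclude it. Picking the significant outcome afterwards has the same effect.

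- Three independent tests, each exactly at 5%: 1 − 0.95³ = 14.3%.
- Viability tested at both time points, four independent tests: 1 − 0.95⁴ = 18.5%. Two readings of the same flap are correlated, so the real figure would be lower.

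With rare events the chi-square test rejects less often than 5%. The exact size of the uncorrected Pearson test at 53 versus 53 is:

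| Event rate | 1% | 2% | 5% | 10% | 20% | 30% |
|---|---|---|---|---|---|---|
| Size | 0.0023 | 0.0148 | 0.0443 | 0.0493 | 0.0510 | 0.0523 |

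The maximum is 0.0533, at about 37%. The three-test rate is 1 − 0.95 × (1 − size for viability) × (1 − size for seroma). The correlated column is a simulation of 100,000 trials with latent correlation 0.8 among all three outcomes.

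| Necrosis, seroma rate (assumed) | Independent | Correlation 0.8 |
|---|---|---|
| 1%, 2% | 6.6% | 6.5% |
| 2%, 2% | 7.8% | 7.8% |
| 2%, 5% | 10.6% | 10.0% |
| 5%, 10% | 13.7% | 12.6% |
| 10%, 20% | 14.3% | 12.7% |
| 20%, 30% | 14.6% | not run |

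With both chi-square sizes at their maximum the independent figure is 14.9%.

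If viability is compared in its four grades, the simulated size of the 2×4 test runs from 0.002 (split 97/1/1/1) to 0.043 (split 70/15/10/5). With seroma at 2 to 20%, the three-test rate is then 6.6 to 13.8%.

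**Step 4. What 53 per group can detect, for choosing a primary outcome.** At two-sided 0.05 and 80% power:

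- t test on VAS: a mean difference of about 0.55 SD.
- Chi-square on a binary outcome: about 5% versus 23%, or 2% versus 17%.

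**The case against.** The strongest objection is that the inflation rests on a rule the protocol never states. Three outcomes, each reported at 0.05 as its own question, is a fair reading of the objectives and the analysis section, and any adjustment could sit in an analysis plan not shown. This stands as far as the 7 to 15% is concerned, which is why that figure is conditional. It does not remove the defect: on that reading the single hypothesis has no deciding result, and naming the outcome that answers it belongs in the protocol.

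A second objection is that the figures depend on the uncorrected chi-square and on assumed event rates. With Fisher's exact test for the two binary outcomes, the three-test rate would be only about 5% (2%, 2%) to 9.6% (10%, 20%). That is correct arithmetic, but the protocol specifies chi-square and gives no small-cell rule. In the other direction, counting viability twice raises the ceiling to 18.5%. The range is an illustration, not a bound.

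Third, the rationale is largely cosmetic and the VAS is patient-rated, so patient-rated cosmesis may be the intended priority. That is plausible, but it is inference: the protocol never says so, and it sizes the trial on a proportion while analysing a mean.

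**Conclusion.** The concern holds. The protocol has one hypothesis, three unranked outcomes tested at 0.05 (four comparisons if viability is tested at both times), and a sample size built on a quantity it does not analyse. The outcome that carries the conclusion is therefore open to choice after the data are seen. This rests on the text alone and needs no assumption.

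The numerical size is conditional. If any one significant result is taken to confirm the hypothesis, the error rate is about 7 to 15% for three tests. The protocol gives no event rates, grade splits or correlations, so all of these are assumed. If the outcomes are reported as separate questions, no inflation is claimed.

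The data would remain usable, and the remedy is cheap but works only if made before results are known. It should be corrected.

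**What to change.** Before analysis, amend the protocol to name one primary outcome, at one time point, with one test at two-sided 0.05, and state that the hypothesis is judged on it alone. The choice is the sponsor's; patient-rated VAS on day 7 by t test is one example. List the other outcomes, including any further viability time point, as secondary.

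Rewrite the sample-size paragraph for the chosen outcome. If 106 patients is kept, state what that number can detect. At 53 per group a rare binary event would be a weak choice, because only large differences are detectable.

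Naming the outcome needs no extra patients, visits or measurements. The price is that an isolated significant secondary result could no longer be presented as confirming the hypothesis.

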15. Emiroğlu M, Sert İ, İnal A. The role of oncoplastic breast surgery in breast cancer treatment. *The journal of breast health*. 2015 ;11(1):1.

Data Collection Proforma

Sr. #: _____ Name: _____ Age: _____ Gender: _____

Marital status: _____ Education status: _____

Residence: _____ Contact #: _____ ,

History of smoking: yes/no, family history of any cancer:
 yes/no _____ 1st degree: _____ 2nd degree: _____ 3rd
 degree: _____, Caste: _____, children: _____ Breast fed: yes/no,

Age of menarche: _____, H/O contraceptive use: _____

Consanguineous marriage: yes/no _____

Menopause: yes/no H/O alcohol use: yes/no, H/O smoking:

Chronic liver disease: yes/no

Chronic renal failure: yes/no

Tuberculosis: yes/no

Inflammatory bowel disease: yes/no

Autoimmune disease: yes/no

Previously treated any cancer disease: yes/no

Breast cancer with pregnancy: yes/no

Diagnosis (histopathology) _____,

Histological grade: I _____, II _____, III _____

Receptors: ER _____ PR _____ Her 2 neu _____ others _____

Stage _____ Chemo status _____

Surgery type _____ Radiotherapy _____

Variable	Group A (grisotti flap)		Group B (reverse mirror grisotti flap)	
Flap viability (A-D)	At 48 hours	On 7 th post-op day	At 48 hours	On 7 th post-op day
Cosmetic outcome (visual analogue scale)				
Seroma formation On 7 th post-op day	Yes / No		Yes / No	

Informed Consent Form

COMPARISON OF OUTCOME BETWEEN GRISOTTI FLAP VERSUS REVERSE MIRROR GRISOTTI FLAP FOR CENTRAL QUADRANT BREAST TUMORS.

The doctor has explained me about my disease. The research modalities required for treating my tumour have been thoroughly explained to me. As this research work requires the utilization of either grisotti or reverse mirror grisotti flap technique, therefore I allow the doctor to utilize any of these procedures on me.

